## Appendix D    Sample SAS® code for supportive analyses for missing data of primary efficacy endpoint

```
* VARIABLES;
* cnsrn - censoring indicator, cnsrn=1-cnsr with 1=event, 0=censor;
* adt - event or censoring date;
* rfstdt – randomization date
* EOSSTT – whether patients completed or discontinued from study;
* EOTSTT – whether patients either completed or discontinued from treatment;
* TRTEDT – treatment end date;* armn – treatment arm, 0 for control;
* planned_closeout_date – planned closeout visit date for patients without closeout visit

data sce1 sce2 sce3 sce4;
  set &data;
  aval_trted= adt-trtedt+1 ;

  ** subjects are treatment completer**;
  if EOTSTT ^= 'DISCONTINUED' THEN output sce1;
  *** 2a: subjects with MACE before IMP discontinuation; 2b:
  subjects with first MACE after IMP disct and study completer ***;
  if (EOTSTT='DISCONTINUED' and CNSRN=1 and ADT<=TRTEDT ) OR
  (EOTSTT='DISCONTINUED' and CNSRN=1 AND ADT>=TRTEDT and
  EOSSTT^="DISCONTINUED") then output sce2;
  *** subjects discontinued IMP and study, 3a: first MACE after
  pEOS, 3b: first MACE after pEOS ***/;
  if EOTSTT='DISCONTINUED' AND EOSSTT = 'DISCONTINUED' AND CNSRN=1
  AND ADT>=TRTEDT then output sce3;
  *** 4: subjects of discontinued treatment and study without MACE
  by study closeout visit ***;
  if EOTSTT='DISCONTINUED' AND EOSSTT='DISCONTINUED' and CNSRN=0
  THEN OUTPUT SCE4;
run;

*** combine scenario 2 and 3 to estimate hazard rate **;
data pattern1;
  set sce2 sce3;
run;

proc sort data=pattern1;
  by armn;
run;

ods output PosteriorSample = PostSamp;
proc phreg data = pattern1;
  model aval_trted*cnsrn(0)=;
  ** Number of imputation times = nmc/thinning = 100 times;
  bayes seed=14828 piecewise=hazard (ninterval=1 prior=gamma)
  nbi =2000 thinning=10 nmc=1000;
  by armn;
```

```
run;

/*proc print data=postsamp;
run; */

proc sort data=postsamp;
  by armn;
run;

data parout;
  retain _imput_ ;
  set PostSamp;
  by armn;

  if first.armn then
    _imput_=0;
    _imput_= _imput_ +1;
run;

DATA PATTERN2;
  SET SCE4;
RUN;

proc sort data=PATTERN2;
  by armn;
run;

proc sql;
  create table pattern2_a as
  select *
    from pattern2 as r full join parout as l
      on r.armn=l.armn;
quit;
*****;
data tempdata;
  set pattern2_a;
  by armn;
  *** Note: Simulate time to event. As a sensitivity analysis,
  multiply hazard (lambda) for treated subjects by the delta1 ***;

  if armn=1 then
    _lbdcur=Lambda1*1;
  else _lbdcur=Lambda1*&delta1;
    Scens=1*exp(-1*(adt-trtedt)*_lbdcur);  ** compute 1-
survival at censored time;
    Fcens=1-Scens;
    u=Fcens+ranuni(14828)*(1-Fcens);  ** simulate uniform r.v
from Fcens to 1;
    imp_censor_date =trtedt - (log(1-u))/_lbdcur;
    format imp_censor_date YYMMDD10.;
```

```
if imp_censor_date > scv then
    do; imp_censor_date = scv;
        imp_censor=0; /*imp-censor: 1 event, 0 further
censored*/
    end;
else
    do; imp_censor=1; end;

run;
/*observed data no missing data first: sce2 and sce3*/
data complete;
    set sce1 sce2 sce3;
    imp_censor=cnsrn;
    imp_censor_date=adt;
    _input_=0;
    do i = 1 to 100;
        _input_=_input_+1;
        output;
    end;
run;

/*combine observed data with imputed data (sce4 with missing data)
*/
data imputed;
    set complete tempdata;
    imp_time=imp_censor_date- rfstdt;
    if armn=1 then armpool=1; else armpool=2; /*armpool combine
treatment group 4mg and 6mg in one group*/
    drop loglike logpost u iteration;
run;

/*proc print data=imputed (obs=1000);
var armn armpool;
run; */

proc sort data=imputed;
    by _input_ armpool;
run;

proc phreg data = imputed;
    by _input_;
    class armpool (ref=first) region1 STRATUM;
    model imp_time*imp_censor(0)=armpool region1 STRATUM/risklimits
rl;
    ods output ParameterEstimates=_es;
run;
*****proc sort data=_es;
    by parameter ClassVal0;
run;
proc mianalyze data=_es alpha=0.05;
```

[figure not shown]
```
by Parameter ClassVal0;
  modeleffects Estimate;
  STDERR StdErr;
  ods output ParameterEstimates = _es_mianal;
run;

data mihr;
  set _es_mianal;
  where parameter='armpool'; /*only keep hazard ratio of
treatment*/
  LogHR_mi=Estimate;
  HR_mi=exp(Estimate);
  HR_LCL_mi=exp(LCLMean);
  HR_UCL_mi=exp(UCLMean);
  Delta=&delta1;
  keep Parameter ClassVal0 LogHR_mi HR_mi HR_LCL_mi HR_UCL_mi
Probt delta;
  rename Probt=Probt_mi;

run;
```

Signature Page for [REDACTED]  
efc14828-16-1-9-sap

Approve & eSign

Approve & eSign

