- Step 1: For each arm, the hazard rate after treatment discontinuation will be generated from the posterior distribution of the parameters in the exponential survival function in subjects who have discontinued treatment but either have MACE event prior to scheduled study closeout visit or have completed study.

Note: the Kaplan-Meier curve based on observed pooled data is nearly a straight line, so constant hazard rate is assumed. So exponential survival function is used for hazard rate for each arm.

- Step 2: The missing event date of scenario 4 will be imputed multiple times by the samples of the hazard rate generated in Step 1. The imputed event date will be censored by the planned study close-out visit date if the imputed event date is after the study close out visit date.

- Step 3: In each imputation, the imputed dataset will be analyzed by the same Cox proportional hazards model as the primary analysis.
- Step 4: The results of the above analyses will be combined using Rubin's formula
- A tipping point analysis will be performed, where time to events will be imputed by using the same multiple imputation method as described above (step 1-4) and vary the hazard rates for subjects not complete study and have missing MACE event. The goal of the analysis is to find the scenarios where the result from the primary endpoints analyses will be “tipped”, i.e., the conclusion of non-inferiority will change. More specifically, a grid-search with hazard rates for the efpeglenatide group increased by an increment (e.g. 1, 1.1, 1.2, 1.3, 1.4, 1.5, 1.6, ...) will be implemented to explore the plausibility of missing data assumptions. A proper range of the hazard rates will be searched to estimate the point where the upper bound of 95% CI for the hazard ratio exceeds 1.3, and 1.8 respectively, when the corresponding comparison fails to declare statistical significance for non-inferiority.

SAS pseudo-codes is provided in [Appendix D](#).

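### SAP Appendix D contradicts itself on which arm code is control, so the missing-data and tipping-point code gives the intended comparison only if its own header is wrong

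*SAP*

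**What the plan says.** SAP 2.3.4.1.3 (Assessment of missing data) describes a four-step multiple imputation for patients who left the study without a MACE, followed by a tipping-point analysis, "a grid-search with hazard rates for the efpeglenatide group increased by an increment". Step 2 caps imputed dates at the planned study close-out visit date. Step 3 analyses each imputed dataset with the primary Cox model. SAP 2.3 allows formal testing only of pooled efpeglenatide against placebo. The section refers to Appendix D for the code.

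In Appendix D:
- The variable list gives "armn – treatment arm, 0 for control". It gives no codes for 4 mg and 6 mg.
- A comment states the purpose of delta: "multiply hazard (lambda) for treated subjects by the delta1".
- The hazard of arm 1 is left alone ("lbdcur=Lambda1*1"). Every other arm gets "else _lbdcur=Lambda1*&delta1;".
- Pooling is done by "if armn=1 then armpool=1; else armpool=2", with a comment that this combines 4 mg and 6 mg.
- The model statement is "class armpool (ref=first) region1 STRATUM", so group 1 is the reference.
- The cap is applied by "if imp_censor_date > scv then". The variable list does not contain scv. It does contain planned_closeout_date, described as being for patients without a close-out visit, and the code never uses it.

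**The concern.** The header and the two if/else lines cannot both be right. The analysis asks how much worse unobserved outcomes on efpeglenatide would have to be before non-inferiority is lost. It answers that only if delta falls on the two efpeglenatide arms and placebo alone is the reference.

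The grouping line runs after observed and imputed data are stacked. A wrong code would therefore misassign every patient in the dataset, and would affect the delta = 1 imputation result as well as the search over delta.

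Three smaller gaps sit in the same code: the undeclared cap variable, a two-level treatment term where Step 3 promises the primary model, and a group of patients that the scenario split does not pick up.

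**Working it through.** **1. The two lines under each possible coding**

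| Coding of the data | Arms given delta | Reference group | Comparison group |
|---|---|---|---|
| 0 = placebo, doses 1 and 2 | placebo and dose coded 2 | dose coded 1 | placebo + dose coded 2 |
| 1 = placebo, doses 2 and 3 | both doses | placebo | pooled doses |
| 0 = placebo, no dose coded 1 | all three arms | none | all arms in one group, no contrast |

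Only the second row gives the analysis in SAP 2.3.4.1.3, and that row contradicts the header.

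**2. Planning inputs (SAP 1.3)**

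The SAP assumes placebo rates of 4.4%/yr without and 3.7%/yr with an SGLT2 inhibitor; a 15% reduction without and no effect with one; 20% use at baseline, plus 10% on placebo and 5% on efpeglenatide; 330 events; and 1:1:1 allocation. Counting add-on use over the whole follow-up:
- Placebo: 0.70 × 4.4 + 0.30 × 3.7 = 4.19%/yr
- Efpeglenatide: 0.75 × (0.85 × 4.4) + 0.25 × 3.7 = 3.73%/yr
- Hazard ratio: 3.73 / 4.19 = 0.890

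**3. The plan's own figure first**

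Power at margin 1.3 = Φ(√(330 × 2/3 × 1/3) × (ln 1.3 − ln 0.890) − 1.96) = Φ(8.563 × 0.3787 − 1.96) = Φ(1.28) = 90.0%. The stated 90% is reproduced, so these inputs are a fair basis.

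**4. Intended comparison at delta = 1**

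Events split in proportion to the rates, with total 4.19 + 2 × 3.73 = 11.65.
- Placebo: 330 × 4.19 / 11.65 = 118.7. Pooled efpeglenatide: 211.3.
- SE(log HR) = √(1/118.7 + 1/211.3) = 0.1147
- HR 0.890, 95% CI 0.711 to 1.115

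**5. Comparison as coded, with 0 = placebo and a dose at 1**

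- HR = ((4.19 + 3.73) / 2) / 3.73 = 1.062
- Reference dose: 330 × 3.73 / 11.65 = 105.7 events. The other two arms: 224.3.
- SE(log HR) = √(1/105.7 + 1/224.3) = 0.1180
- 95% CI 0.842 to 1.338, so the upper bound exceeds 1.3 before any delta is applied.

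**6. Illustrative simulation**

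The setting was 4000 patients, exponential hazards at the rates above, 2%/yr dropout, 24 to 36 months of follow-up and 400 runs, with an exponential rate ratio in place of the Cox model.

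| Delta | As coded: mean HR, mean upper bound | As intended: mean HR, mean upper bound |
|---|---|---|
| 1 | 1.07, 1.33 | 0.90, 1.11 |
| 5 | 1.16, 1.44 | 0.97, 1.19 |

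**7. The cap variable**

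SAP 2.1 says that patients who left the study early miss the close-out visit, and every scenario-4 patient left early. If scv holds an actual visit date, it is missing for them. SAS ranks a missing value below any number, so the test is true, the imputed date is set to missing, and the Cox procedure drops the patient. If scv already holds the planned date, only the declaration is lacking.

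**8. The scenario split**

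Scenarios 2 and 3 require an event. Scenario 4 requires study discontinuation. A patient who stopped IMP, completed the study and had no MACE meets none of the four output conditions. Step 1 of SAP 2.3.4.1.3 includes these patients. As coded, they enter neither the hazard estimate nor the Cox model.

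**The case against.** The strongest reply is that the header comment is the error and the arm logic is sound. Both if/else lines test for code 1, the code comments assign delta to treated subjects and say the pooling joins 4 mg and 6 mg, and SAP 2.3.4.1.3 assigns delta to efpeglenatide. All of that fits 1 = placebo. The mismatch turns on one digit in a comment line. This reply stands as a real possibility, and it is why the consequence above is conditional.

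Second, Appendix D is labelled sample code and the SAP text calls it pseudo-code. A hazard ratio near 1.06 at delta = 1 beside a primary result near 0.89 would also be conspicuous. Both are fair. But the appendix is the only place that specifies the prior, the seed, the conditional draw and where delta enters, so a programmer would start from it, and the plan requires no reproduction check.

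Third, the intended cap is clear: SAP 2.3.4.1.3 expands SCV as the study close-out visit, and Step 2 names the planned date. That stands, so loss of the scenario-4 patients is a risk only if scv is filled with actual visit dates.

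Fourth, a two-level term and an equal-weight contrast should agree closely when the doses are allocated 1:1, unless the doses differ materially. That also stands. It is a small departure from Step 3.

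**Conclusion.** The contradiction between the header and the code is certain. Its effect depends on dataset coding that the documents do not state. With 0 = placebo and a dose at 1, the supportive analyses would compare placebo plus one dose with the other dose, at about 1.06 (0.84 to 1.34) instead of 0.89 (0.71 to 1.11). These figures rest on the planning rates, 330 events, constant hazards and equal effects of the two doses. With 1 = placebo, the arm logic has no numerical error.

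A reader might infer three stronger things that the documents do not support:
- That delta will in fact be applied to placebo. The dose codes are not given, and the code comments point the other way.
- That no tipping point could ever be found. This needs scv to be missing for scenario-4 patients, which the SAP does not say.
- That the non-inferiority test itself is compromised. The primary Cox analysis in SAP 2.3.4.1.1 names its treatment groups and does not use this code. In the worked example the miscoding also pushes towards failing non-inferiority, so it does not show false support for the drug.

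The point should be corrected because the only operational specification of this sensitivity analysis gives the wrong comparison if its declared coding is followed.

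**What to change.** 1. State all three armn codes in Appendix D. Make the header, the delta line and the pooling line agree with them, so that delta applies only to the two efpeglenatide arms and placebo alone is the reference. Do not simply replace the test with armn = 0: if the data use 1, 2 and 3, that would give delta to all arms and leave no contrast.
2. Cap imputed dates explicitly at planned_closeout_date instead of scv.
3. Fit the three-level treatment model of SAP 2.3.4.1.1 and combine the pooled contrast across imputations, as Step 3 says.
4. Output the patients who stopped IMP, completed the study and had no MACE, and include them in the hazard estimate and the analysed dataset.
5. Require a check that, with scenario-4 patients left out, the code reproduces the primary-model hazard ratio on the same patients. This check can pass only once item 4 is done.

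The cost is a few code lines and one test run before database lock, with no change to data collection or to the primary analysis.

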#### Assessment of missing data

For patients who discontinued study but no MACE event was positively adjudicated by scheduled study closeout visit, the missing data are events that may occur after a patient is censored (the later of the patient's study discontinuation date and the last date they have information on CV efficacy endpoint for patients who discontinued the study).

[figure not shown]
Reasons for censoring (including non-CV death, completed study, and study discontinuation reasons) will be summarized. For patients who discontinued the study, the time from censoring date to planned study close-out visit date will be summarized to show the magnitude of missing information.

Subjects prematurely and permanently discontinuing IMP, for other reason than death, prior to study end could have a different event and hazard rate from those who stay on IMP throughout the study, and their corresponding dropout could be considered informative. This subgroup can be divided into subjects with information and subjects with missing information regarding primary MACE endpoints, see figure below.

Diagram showing subjects divided into subgroups related to missing information about MACE.

Subjects with information related to the MACE endpoint events (either discontinued study but have MACE prior to scheduled study closeout visit, or completed the study) will be used to impute data in subjects without MACE endpoints (discontinued study and no MACE event reported through third party data by scheduled study closeout visit). Subjects who developed MACE prior to the IMP discontinuation are included for imputation and their time to MACE data will be used for the imputation modeling. With these subjects included, the model estimate of hazard should fully reflect the potential hazard of the subjects with missing outcome. More specifically, subjects from below scenarios 2 and 3 will be used to impute the missing data of scenario 4 of the same treatment arm:

Note:

1. SCV: study close-out visit;
2. MACE censoring date of scenario 4 is the later of study discontinuation date or latest date with CV event information collected

The following supportive analyses will be performed to evaluate how the primary efficacy results could be influenced by different assumptions about the missing data. In particular, a 4-step approach will be used:

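### The Appendix D code fits the imputation hazard to event cases only and loses event-free IMP-discontinuers who completed the study, contrary to the SAP text it is meant to implement

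*SAP*

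**What the plan says.** SAP section 2.3.4.1.3, Assessment of missing data, describes a four-step imputation for participants who left the study without a known MACE (scenario 4). Donors are IMP-discontinuers who "either discontinued study but have MACE prior to scheduled study closeout visit, or completed the study". Step 1 fits an exponential hazard per arm in "subjects who have discontinued treatment but either have MACE event prior to scheduled study closeout visit or have completed study". The same section says that participants whose MACE came before IMP stop also contribute to the imputation model.

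Step 3 reads: "In each imputation, the imputed dataset will be analyzed by the same Cox proportional hazards model as the primary analysis". That primary analysis is ITT, with all randomized participants (SAP 2.2.3.1 and 2.3.4). A tipping-point analysis then raises the efpeglenatide hazard to find "the point where the upper bound of 95% CI for the hazard ratio exceeds 1.3, and 1.8 respectively".

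For the implementation the section says "SAS pseudo-codes is provided in" Appendix D. There, the branch of `sce2` for participants still in the study at its end requires "EOTSTT='DISCONTINUED' and CNSRN=1 AND ADT>=TRTEDT and" study not discontinued. The donor set is described as "combine scenario 2 and 3 to estimate hazard rate", and the observed part of the Cox data is built with "set sce1 sce2 sce3".

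**The concern.** In the code, `CNSRN=1` means an event. Every route into `sce2` and `sce3` requires it, so the event-free study completers named as donors in Step 1 cannot enter the hazard fit. They do not qualify for `sce1` (IMP not stopped) or `sce4` (study discontinued) either.

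This is the SAP's only imputation-based check that non-inferiority survives missing follow-up. If its starting hazard is far too high, most scenario 4 participants become events before any penalty is applied, and the tipping multiplier has little room to act. Because IMP-discontinuers with an event are kept and event-free completers are dropped, a modest arm difference in IMP stopping can also move the hazard ratio by itself.

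**Working it through.** **Design figures.** Counting all add-on SGLT2 inhibitor use, the SAP 1.3 inputs give an average hazard ratio of (0.75×4.4×0.85 + 0.25×3.7)/(0.70×4.4 + 0.30×3.7) = 3.73/4.19 = 0.890. Events for 90% power at margin 1.3 with 2:1 allocation: (1.960 + 1.282)² / [(1/3)(2/3)(ln(0.890/1.3))²] = 330, as stated. The imputation count, 1000/10 = 100, also agrees. The point does not depend on either figure.

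**Routing.** All combinations of IMP status, study status, event and date order (24) were traced through the IF statements:

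| IMP stopped | Study stopped | Event | Data set |
|---|---|---|---|
| no | either | either | `sce1` |
| yes | no | yes | `sce2` |
| yes | no | **no** | **none** |
| yes | yes | yes | `sce2` (event on or before last dose) or `sce3` (on or after) |
| yes | yes | no | `sce4` |

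Only the third row is lost. A study-discontinuer's event dated on the last dose enters both `sce2` and `sce3` and is duplicated. The SAP counts death in study as completion, so non-CV deaths after IMP stop are also lost if `EOSSTT` is coded that way.

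**Hazard by hand.** The exponential estimate is events divided by person-time. With events only, it is 1/(mean event time). If follow-up after IMP stop is uniform on 0 to 2.5 years and events are rare, the mean event time among cases is 2.5/3 = 0.833 years, so the hazard is 1/0.833 = 1.2 per year almost whatever the true risk. The SAP's placebo rates are 4.4% and 3.7% per year.

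Now take an assumed IMP stop of 10% per year and SAP follow-up. One simulation gives about 42 events after stop and 760 event-free completers.

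- Code: 42 events over 42/1.2 = 35 person-years.
- Text: add 760 × 1.25 years = 950 person-years. The hazard is 42/985 = 0.043 per year.

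**Imputed events by hand.** About 184 participants are in scenario 4. With remaining time uniform on 0 to 2.5 years:

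- Code: 1 − (1 − e^(−3))/3 = 0.683, or about 126 events.
- Text: 1 − (1 − e^(−0.107))/0.107 = 0.051, or about 9 events.

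If delta turned all of the active two-thirds (123) into events, the code could reach only 123 + 61×0.683 = 165, or 39 more. The text has room for about 117 more (123 + 3 − 9).

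**Simulation.** The documents give no IMP-stop rate, so it was varied. The listing was first made executable: one imputation index, `scv` taken as planned close-out, placebo as the unmultiplied reference, and non-positive times excluded. Sixteen settings covered IMP stop of 5 to 20% per year, study discontinuation of 1 to 4% per year, and 0 to 70% of events found after withdrawal. Central settings (24 to 36 months, 2% per year study discontinuation, 30% found):

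| IMP stop per year | Hazard, code / text | Event-free lost | Events imputed, code / text |
|---|---|---|---|
| 5% | 1.20 / 0.050 | 260 | 108 / 10 |
| 10% | 1.19 / 0.045 | 630 | 113 / 9 |
| 20% | 1.16 / 0.042 | 1262 | 107 / 8 |

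Over all settings the median hazard ratio of code to text was 23 to 33. A second, simpler simulation gave 1.15 to 1.27 against about 0.04 per year, 126 to 129 against 9 to 10 imputed events, and 405 to 1068 lost at 5 to 15% IMP stop.

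**Tipping point** (median upper bound, 100 trials):

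| IMP stop, placebo / active | Version | Delta 1 | Later values | Reaches 1.3 |
|---|---|---|---|---|
| 10% / 10% | text | 1.09 | 1.24 (8), 1.30 (12) | about 12 |
| 10% / 10% | code | 1.13 | 1.25 (5), 1.28 (20) | not by 20 |
| 8% / 10% | text | 1.10 | 1.26 (8), 1.31 (12) | between 8 and 12 |
| 8% / 10% | code | 1.23 | 1.29 (2), 1.33 (3) | between 2 and 3 |

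**Scenario 2a.** The code sets time as `adt-trtedt+1`. A MACE before IMP stop then has time zero or less, so a time-since-stop model cannot use it, although the text says it contributes.

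**The case against.** The SAP text is clear and right about the donors. The listing is labelled sample or pseudo-code, the production program may differ, and the analysis is only supportive. That limits the reach of the error but does not remove the contradiction, because the SAP cites this listing as the implementation.

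The simulated code results come from a listing repaired to run. Read literally, the imputed rows carry `_imput_` while the Cox step runs by `_input_`, so they would fall outside the 100 fits. This name difference may come from reading the PDF and should not be counted as an error. The figures therefore measure the donor rule and the lost group, not every printed line.

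The loss of non-inferiority at delta 1 is sensitive to modelling. With IMP stop at 8% against 10% per year, the main simulation kept non-inferiority in 64% of trials under the code (91% under the text), and another run gave 65 to 73% under the code. A rerun with blended hazards and no events found after withdrawal gave 89% (96% under the text), a code bound of 1.18, and 1.25 at delta 2. With equal stopping, both bounds stay well below 1.3 at delta 1, so the error does not by itself reverse non-inferiority. No single percentage should be relied on. The inflated hazard and the distorted tipping point appear in every run.

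The text version used for comparison leaves out pre-stop MACE from the fit, because a time-since-stop model cannot take them. The 23- to 33-fold ratio is therefore to the workable part of the written method.

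**Conclusion.** The concern holds. That the hazard is fitted to events only, and that event-free study completers who stopped IMP reach no data set, follows from the IF statements and needs no assumed rate. Both contradict Steps 1 and 3.

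The size rests on assumed IMP-stop rates and timing: a hazard roughly 23 to 33 times too high, hundreds of participants lost, and in the central settings more than 100 imputed events instead of about 10. The tipping point can reassure falsely (not reached by delta 20 instead of about 12) or alarm falsely (reached between delta 2 and 3 instead of between 8 and 12). The primary Cox analysis is not affected.

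**What to change.** Before database lock:

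- Output `EOTSTT='DISCONTINUED'`, `EOSSTT^='DISCONTINUED'`, `CNSRN=0` to its own data set. Add it to `pattern1` as censored time since `TRTEDT`, and to `complete`.
- Reconcile scenario 2a between text and code. The simplest course is to keep MACE before IMP stop as observed events in the Cox data, leave them out of the time-since-stop fit, and say so in 2.3.4.1.3.
- Reconcile the variable header (`armn` 0 is control) with the executable lines that treat `armn=1` as the unmultiplied reference, so that delta applies to both efpeglenatide arms and only to them. Confirm one imputation index name and add `scv` to the variable list.
- Add a check that each imputed data set holds every ITT participant exactly once. This also catches the `ADT=TRTEDT` duplicate.

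Optionally, count scenario 4's observed event-free time after IMP stop in the hazard. The cost is a few lines of code and one sentence of SAP text, with no new data. If the production program already follows Step 1, only the appendix and the scenario 2a sentence need correcting.
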